## 12.0 Data Management

Power: Dose-response studies are not powered in the traditional manner. To resolve the shape of the continuous dose response function, it is statistically more efficient to select more doses as opposed to more participants (O’Quigley & Conaway, 2010; Kuljus et al., 2006). The number of observations within each dose primarily accounts for sampling variability, which could be achieved with 2-3 observations. Capturing variability is essential to the planned analyses, which underweight the points of greatest variability in estimating the response curve. Thus, the sample size of  $N = 45$  was determined sufficient to accomplish Aim 1 to establish a dose-response curve. Of note, [name] is running three funded projects with these dose-response techniques in optimizing repetitive transcranial magnetic stimulation (rTMS). An additional, sample of 45 participants are included in the case of data loss and to replicate dose-response findings/assess feasibility/tolerability on participants with anxiety or trauma related disorder or symptoms.

Analyses: The psychophysiological data will be processed using standard protocols which have previously been used in this lab and in various other studies (Sege et al., 2017, 2018, Taylor et al., 2020; Grant et al., 2015), and according to published guidelines (Blumenthal et al., 2005; Boucsein et al., 2012; Gatchel et al., 1973; Keil et al., 2014).

Dose-response relationships will be assessed using the multiple comparisons procedure with modeling (MCP-Mod) approach pre- to post-stimulation changes in physiology and behavior. To determine the reliability of a dose response, MCP-Mod fits a set of pre-specified candidate dose-response curves to the data using a multiple-comparisons technique. The pre-specified dose-response curves to be tested would be Emax, logistic, and linear. Significant curves would then be used to develop inferences on optimal doses for a follow-up adaptive-dosing design, with doses more finely resolved around the probable point of maximal efficacy as determined in this project.

**Confidentiality and Quality Control:** All study personnel will complete Social-Behavioral-Educational research CITI training, and also complete in-lab training regarding data security practices. Study personnel will be trained in the IRB protocol. The investigator, and co-investigators will be available to monitor data collection to ensure quality, confidentiality, and adherence to the IRB protocol.

The majority of this study's procedures will take place in the study's research suite, which is a private room with limited access. Regarding documentation, participant names will appear only on the IRB-approved Consent, HIPAA, and payment forms. After the participant electronically signs the consent form on HIPAA-compliant RedCap, a random identification code will be assigned to the individual, and all data collection will be referenced to the code rather than name or other identifying information. Questionnaires will be completed in a HIPAA-compliant RedCAP interface. There is some risk to loss of confidentiality due to the remote nature of consent and questionnaires. It cannot be guaranteed that participants will complete these study portions in private spaces, though they will be encouraged to do so for their protection. Payment forms will be collected and stored separately from data in a locked cabinet for up to 6 years.

After participation, RedCAP data will be downloaded in excel format to the secure MUSC server. Finally, physiology data files will also be linked only to participant code; these data will be recorded on password-protected local drives at the IOP.

In terms of publication, data will be published in aggregate form, so individual participants will not be identifiable in the final manuscript. No identifying information will be published.

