In order to develop therapeutic taVNS for psychiatric problems, a necessary first step is to establish the appropriate parameters that will modulate cognitive and affective responses among healthy participants. We will first recruit 45 healthy participants (randomized to 9 different dose durations) to determine the dose-response curve for taVNS on a range of vagally-mediated physiological measures and subjective mood. At a single session, heart rate variability (HRV), skin conductance (SC), and electroencephalography (EEG) will be measured at baseline, concurrently with stimulation, during learning and cognitive tasks and finally during a recovery period. Utilizing rest, learning and recovery conditions concurrent with multiple physiological measures we will demonstrate whether there is process- or physiological modality-specific modulation or co-activation across domains and measures. Our team of experts in brain stimulation, neuroscience, and psychophysiology are uniquely suited to accomplish these tasks. After establishing the dose-response curve, the findings of our dosing may be evaluated an additional sample of 45 participants seeking treatment for anxiety or trauma related disorder.

An additional goal of this study is to evaluate invasive vagus nerve stimulation (VNS) to determine how taVNS relates to other established forms of brain stimulation via the vagus nerve. VNS is currently FDA approved for depression and epilepsy, and research has indicated that patients also report decreased anxiety symptoms. Therefore, patients with previously implanted VNS, will be invited to complete this study. They will be administered similar tasks as participants who receive taVNS, and a full psychophysiological profile will be assessed. This study will only recruit individuals who currently have implanted VNS, given the invasive procedure. Although VNS is FDA approved, nearly 150,000 patients have received VNS worldwide over the past 25 years. Therefore, limited patients in the study area have received VNS, so this study expects to recruit <5 patients for this study goal.

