Participants will be randomized to one of 9 dose durations with 5 participants per dose, increasing in 10 minute increments of active stimulation, ranging between 10 and 90 minutes of stimulation. All active sessions per dose will be delivered contiguously and at the end of the stimulation period, and sham stimulation at the beginning. This is to ensure that all participants have the same lapse of time between pre- and post-stimulation recording. That is, if a participant is randomized to 60 minutes of active stimulation, the first 30 minutes would be sham stimulation. After establishing the optimal dose-duration a sample of treatment seeking individuals will be recruited. This dose will be administered to individuals with anxiety and trauma symptoms to ensure that effects are sustained and to determine feasibility and tolerability.

An additional group of individuals with implanted VNS also will be evaluated after 30 minutes of stimulation. Patients at MUSC who participated in the Microtransponder Vivistim trial or other research/treatments involving VNS will be recruited to complete similar cognitive and affective tasks while psychophysiological responses are measured across 3 sessions: control (no stimulation), implanted VNS, and noninvasive taVNS. This will serve as a comparator for whether taVNS is activating similar brain and physiological regions as invasive forms of vagus nerve stimulation. This will also indicate whether mechanisms of taVNS and VNS are comparable. In order to truly determine comparability of these two forms of VNS, it is imperative to assess within subject brain, body, cognitive, and emotional responding across both implanted and non-invasive VNS.

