## **6.0 Number of Subjects**

This study will recruit 90 community individuals who meet the above inclusion and exclusion criteria, 50% of which will be female. Participants ( $n = 45$ ) who are healthy controls will be recruited to establish the dose response curve. Then this dose will be administered to 40 individuals with anxiety and trauma related symptoms. Participants with implanted VNS ( $n = 5$ ) will be recruited for similar procedures.

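### Section 12.0 calls N = 45 sufficient to establish the dose-response curve but states no detectable difference, and a design of this size does not reliably identify the curve's shape

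*Combined protocol and SAP*

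**What the plan says.** Section 1.0: "We will first recruit 45 healthy participants (randomized to 9 different dose durations". Section 3.0: "Participants will be randomized to one of 9 dose durations with 5 participants per dose", with durations "ranging between 10 and 90 minutes of stimulation" in 10-minute steps.

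Section 12.0 opens its power paragraph with "Dose-response studies are not powered in the traditional manner". It argues that adding doses is more efficient than adding people for learning the shape of the curve. On numbers per dose it says: "The number of observations within each dose primarily accounts for sampling variability, which could be achieved with 2-3 observations". It concludes that N = 45 "was determined sufficient to accomplish Aim 1 to establish a dose-response curve".

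The analysis paragraph of the same section tests three candidate curves (Emax, logistic, linear) by MCP-Mod on pre-to-post changes. It continues: "Significant curves would then be used to develop inferences on optimal doses for a follow-up adaptive-dosing design".

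On what follows, Section 6.0 says: "Then this dose will be administered to 40 individuals with anxiety and trauma related symptoms". Section 3.0 is equally unconditional about giving the chosen duration to symptomatic participants. Section 1.0 is permissive: the dosing findings may be taken into a second sample.

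**The concern.** MCP-Mod begins with a multiplicity-adjusted significance test. If significant curves are what feed the dose inference, the design has a power that can be calculated, whatever is said about traditional powering. Efficiency from having many doses does not supply that figure, and Section 12.0 does not give it. The claim to establish the curve goes further, because it needs the candidate shapes to be told apart and not only a trend to be detected.

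Two misreadings are at stake. In a study described as sufficient, a non-significant result could be taken as evidence of no dose-response. A single selected curve could be taken as an established shape and used to place doses in the next study. The sections also disagree on what happens to the second cohort when no curve is significant.

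**Working it through.** **The plan's own figure.** 9 durations x 5 people = 45, so the head count reproduces. Sufficiency cannot be reproduced because no alpha, effect, SD, power or precision target is given. The additional 45 in Section 12.0 are no reserve for Aim 1, since Section 6.0 allots all of them (40 symptomatic + 5 with implants = 45).

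**Inputs.** From the documents: doses 10, 20, ..., 90 minutes; n = 5 per dose; the three candidate families; MCP-Mod. Assumed, because the documents are silent: common variance; Emax ED50 of 20 minutes; logistic midpoint 50 and scale 10 minutes; one-sided alpha of 2.5% or 5% controlled over the three curves. The effect is the difference D between the 90- and 10-minute means, in SDs of the change score.

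**Detection.** Each optimal contrast gives a t statistic on 45 - 9 = 36 df. For the contrast matching the true shape, the noncentrality is D x sqrt(5 x S), where S is the sum of squares about the mean of the nine means scaled to run from 0 to 1. For the linear shape S = 60/64 = 0.9375, giving sqrt(4.6875) = 2.165 per SD. The critical value for the maximum of the three statistics is 2.21 at one-sided 2.5%. Simulated power, as a range over the three shapes:

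| D (SD) | One-sided 2.5% | One-sided 5% |
|---|---|---|
| 0.5 | 16-23% | 26-34% |
| 0.8 | 35-50% | 48-64% |
| 1.0 | 50-70% | 63-80% |
| 1.2 | 65-84% | 77-91% |
| 1.5 | 84-96% | 91-98% |
| 2.0 | 98% or more | 99% or more |

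80% power is reached at these differences:

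- One-sided 2.5%: about 1.15 SD (logistic), 1.35 SD (linear), 1.4 SD (Emax).
- One-sided 5%: about 1.0, 1.2 and 1.25 SD in the same order.
- One person lost per duration (N = 36), one-sided 2.5%: about 1.3-1.6 SD.

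Cross-check without simulation: a plain linear slope test (43 df, two-sided 5%) has noncentrality 1.083, 1.732, 2.165 and 2.598 at 0.5, 0.8, 1.0 and 1.2 SD, giving power of 18%, 39%, 56% and 72%.

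The argument from two to three observations per dose does not bear on detection. With two per dose, power at 1.0 SD is only 20-29% at one-sided 2.5%.

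**Precision.** The sum of squares of dose is 5 x 6,000 = 30,000. The 95% half-width for the fitted linear 10-to-90-minute change is t(0.975, 43) x 80 / sqrt(30,000) = 0.93 SD.

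**Shape.** The three assumed contrasts correlate 0.89-0.98, so they are nearly the same test. At D = 1.3 SD, among significant results at one-sided 2.5%:

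- By AIC, the true curved family is chosen in about 18-33% of trials. The spread covers Emax versus logistic truth and how finely the curves are fitted.
- By largest contrast, it is chosen in about 65% (Emax) and 58% (logistic). A truly linear curve is called linear in about 40%.

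At 2.0 SD, where detection is nearly certain, AIC still chooses the true Emax in about 44-46% and the true logistic in about 29-35%. With a true Emax ED50 of 20 minutes, the 5th to 95th percentiles of the fitted ED50 reach both ends of the search grid (1 and 135 minutes), even at 2.0 SD.

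**Second cohort.** Section 1.0 makes the second stage optional; Sections 3.0 and 6.0 state it as settled. None says what happens if no curve is significant.

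**The case against.** The strongest reply is that Section 12.0 claims no detection rate. It says only that traditional powering is not used and gives an argument from the number of doses, and Section 16.0 calls the study a pilot meant to inform larger work. That stands, and so do the limits it puts on four stronger readings:

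- A reader might infer that 45 people cannot detect a dose-response. The documents give no effect size or SD, and power is adequate for differences above about 1.0-1.4 SD, depending on alpha and shape. Detection is unsupported, not shown to fail.
- A reader might infer that a non-significant result is the likely outcome. That too needs an effect size which the documents do not give.
- A reader might infer that a straight line would be the default choice. That follows from AIC, which penalises the extra parameters of the curved models and which Section 12.0 does not mention. The largest-contrast rule does better, more so at larger differences. It is also flattered here, because the assumed contrasts match the truth exactly.
- A reader might infer that significance gates the symptomatic cohort. Section 12.0 links significant curves to a later adaptive-dosing design, and Aim 3 concerns tolerability and feasibility. What remains is inconsistent wording and an unstated fallback.

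Nor is there a miscalculation: no power figure is stated that could be wrong. The reply does not rescue the sufficiency claim. Having many doses can be a fair design argument, but it provides neither power for the test nor discrimination among these three curves.

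**Conclusion.** The point holds as a missing justification together with an overstated capability. Whether 45 people suffice to detect a dose-response depends on inputs that the plan does not give. Under the assumptions above, detection at 80% power is limited to large differences between the shortest and longest duration: about 1.15-1.4 SD at one-sided 2.5%, or 1.0-1.25 SD at one-sided 5%. Other curve parameters or unequal variances would move these figures.

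The claim about shape is the weaker part. Under either selection rule, the true family is missed in a substantial share of significant trials at 1.3 SD: about two-thirds or more by AIC, and about 35-42% by largest contrast when the truth is curved. The study can be informative about a trend, but it should not be described as establishing which curve applies.

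**What to change.** 1. In Section 12.0, replace the sufficiency sentence with a conditional one: with 45 participants, MCP-Mod at the stated alpha and sidedness has 80% power for the named endpoint if the 90-minute response exceeds the 10-minute response by a stated number of SDs of the change score. Compute that number from the sponsor's own candidate parameters and state them. The figures above are illustrations and should not be copied in as fact.
2. Add that the shape of the curve will not be reliably distinguished at this sample size.
3. Report the Aim 1 curve and any dose inference as an estimate averaged over the candidate models, with a confidence band. A non-significant result is then not read as no dose-response, nor one selected curve as an established shape.
4. Reconcile Section 1.0 with Sections 3.0 and 6.0, stating before analysis whether, and on what basis, the second cohort proceeds if no curve is significant. That decision is the investigators'.

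Cost: protocol and analysis wording, slightly more analysis work, and a less favourable stated capability. No extra participants are needed.

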EEG will be measured using a 32-channel BrainVision actiCHamp system. Data will be processed with BrainVision Analyzer software. Resting EEG will be measured pre-, post-, and concurrently with stimulation, and will be explored for taVNS dose dependent modulation in frequency bands and coherence of the **EEG power spectrum**. For data collected during the learning/attention task, multiple **event-related potentials** (ERPs) and **steady-state visually evoked potentials** (ssVEPs) will be assessed. A variety of ERPs indicative of attention (i.e., orienting, discrimination) will be evaluated across a variety of contexts after stimulation, including fear learning and extinction, and learning more broadly. Some studies have shown taVNS linked enhancements in the P300, an orienting response (Warren et al., 2020), whereas other studies have not (Warran et al., 2019; Keute et al., 2019). A recent evaluation found taVNS related ERP modulations indicative of enhanced cognitive control (i.e., N2; Pihlaja et al., 2020), which is typically increased during engagement of attention and is enhanced during cognitive conflict. Enhancements in the N2 are typically seen across internalizing disorders, and our previous work demonstrates that the N2 is modulated under internal and external threat (Taylor et al., 2020; Moran, Taylor, & Moser, 2012; White, Grant, Taylor et al., 2018). In addition, ssVEPs which are collected by flickering visual stimuli, may be assessed during stimulation. These potentials are modulated by attentional and motivational factors and will provide real-time dose-dependent data regarding taVNS related modulations in attention. Given the extant and emerging literature on the effects of taVNS on brain activity, these ERPs and other relevant ERPs will be explored.

Participants will complete subjective measures of anxiety and depression and related difficulties as well as Self-Reported Units of Distress (SUDs) during stimulation and the tasks and acceptability/tolerability measures (see Section 10.0 Study Design/Methods for surveys and other measures).

The above measures will also be assessed for participants with implanted invasive VNS and then subsequently with noninvasive taVNS.

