## 10.0 Study Design / Methods

After completing the phone screener, participants will be invited to in-lab participation: they will be provided available times and instructed on how to locate IOP and the laboratory space. They will be asked to refrain from the following prior to the study: Tobacco use within 2 hours, Caffeine within 6 hours, Alcohol within 24 hours, and intense physical activity within 24 hours. Participants will be asked to sleep as they usually do the night before the study. The study will take up to two hours and thirty minutes.

Prior to arrival to the research space, after phone screening, participants will be provided online informed consent (see Section 9.0). After participants have been informed of the nature of the study and consent to the study procedures, they will be sent a series of questionnaires to be completed online using the RedCap survey platform. They will be asked to complete these questionnaires in a private setting to ensure their confidentiality. None of the items on these questionnaires address suicidality. However, surveys will be monitored for extreme scores indicating severe mental health issues or indication of suicidal or homicidal ideation/risk, and those participants will be contacted *immediately* via phone to assess for safety. Several attempts will be made to reach at risk participants. They will be assessed for safety again, upon arrival to the lab. Questionnaires will include a measure of demographics, Penn State Worry Questionnaire (PSWQ; Meyer et al., 1990), the Attentional Control Scale (ACS; Derryberry & Reed, 2002), the Childhood Trauma Questionnaire (CTQ; Bernstein & Fink, 1998), Connor Davidson Resiliency Questionnaire (Connor & Davidson, 2003), Contrast Avoidance Questionnaire (CAQ; Llera & Newman 2017), PTSD Symptom Scale – Self-Report (PSS-SR; Falsetti et al., 1993), the Perseverative Thinking Questionnaire (Ehring et al., 2011), the Social Interaction Anxiety Inventory/Social Phobia Scales Short forms (SIAS-SPS; Fergus et al., 2012), the Intolerance of Uncertainty Scale (Carleton et al., 2007), Difficulties with Emotion Regulation Scale (Gratz & Roemer, 2004), and the Generalized Anxiety Disorder 7-item scale (GAD-7; Spitzer, 2006).

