After all electrodes are attached, a 1) baseline (5-10 min) physiology measurement will be taken. Then stimulation will begin. See additional information in Section 3.0 (Intervention to be Studied). Participants in the taVNS group (not having implanted VNS) will be randomized to one of 9 doses with 5 participants per dose, increasing in 10 minute increments of active stimulation. All active sessions per dose will be delivered contiguously and at the end of the stimulation period, and sham stimulation at the beginning. This is to ensure that all participants have the same lapse of time between pre- and post-stimulation recording. That is, if a participant is randomized to 60 minutes of active stimulation, the first 30 minutes would be sham stimulation.

For participants with previously implanted vagus nerve stimulation devices, stimulation will be delivered for 30 minutes. They will subsequently be invited to revisit the lab to receive non-invasive taVNS delivered in a comparable manner to the healthy subjects for 30 minutes.

Additional physiology measurements will be taken 2) concurrent with stimulation and during a final recovery measurement (5-10 mins) after stimulation has concluded.

During the base, recovery, and during 3 time points during the 90-minute stimulation period (i.e., 30 minutes, 60 minutes, and 90 minutes), a Passive Auditory Oddball Task will be administered. During this task a relaxing movie (i.e., silent sand art film) is presented concurrent with standard and deviant tones; MMN task from the ERP Compendium of Open Resources and Experiments - ERP CORE; Kappenman et al., 2020; Eriksen & Eriksen 1974).

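### MCP-Mod is applied to pre- to post-stimulation change without a baseline covariate, although a baseline is recorded; adjusting for it could gain precision at little cost

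*Combined protocol and SAP*

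**What the plan says.** The only description of the dose-response analysis is in Section 12.0: "Dose-response relationships will be assessed using the multiple comparisons procedure with modeling (MCP-Mod) approach pre- to post-stimulation changes in physiology and behavior". The candidate curves are Emax, logistic and linear. No covariate is listed, and no other section supplies a model.

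A pre-stimulation value exists for the main measures:
- Section 1.0: "heart rate variability (HRV), skin conductance (SC), and electroencephalography (EEG) will be measured at baseline, concurrently with stimulation".
- Section 4.0: "Resting EEG will be measured pre-, post-, and concurrently with stimulation".
- Section 10.0: before stimulation starts, a "baseline (5-10 min) physiology measurement will be taken". For the passive oddball task the timing is "During the base, recovery, and during 3 time points during the 90-minute stimulation period".

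Sections 3.0 and 10.0 randomize participants to nine durations, 10 to 90 minutes, with five per dose. The power paragraph of Section 12.0 also refers to "the planned analyses, which underweight the points of greatest variability in estimating the response curve". That suggests dose-specific weighting, but the plan does not say how the weights are obtained.

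**The concern.** Analysing post minus pre assumes that each unit of difference between two people at baseline carries over fully to the post-stimulation value. If the true within-dose slope is below or above 1, part of the baseline variation stays in the change score as noise. A model that estimates the slope removes it.

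Aim 1 rests on nine means of five people each. Section 12.0 sets N = 45 without an effect size, SD or power figure, and the fitted curves are to guide the choice of doses for a follow-up design. Precision is therefore scarce, and the baseline data that might add some are already being collected. The slope is also likely to differ between measures such as skin conductance and EEG power, so fixing it at 1 for all of them is an assumption that the plan does not discuss.

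**Working it through.** **Inputs from the documents.** 9 doses × 5 participants = 45, which agrees with the stated N. There is no power calculation to reproduce. The error degrees of freedom are 45 − 9 = 36 for the change score and 35 after one common slope is fitted.

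**Assumed inputs.** The pre-post correlation r and the ratio k = SDpost/SDpre. Neither is in the documents.

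**Formulas, pooled variance.** Set SDpre = 1. The slope of post on pre is b = rk and the residual variance is s² = k²(1 − r²).
- Change score: s² + (1 − b)² = 1 + k² − 2rk.
- Baseline-adjusted: s² × 35/34 on average. The extra 1/34 is the price of estimating the slope, the mean of 1/chi-square on 36 degrees of freedom.

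**Equal SDs (k = 1).** The ratio, adjusted over change, reduces to (1 + r)/2 × 35/34.

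| r | Change | Adjusted | Ratio |
|---|---|---|---|
| 0.5 | 1.00 | 0.75 × 1.029 = 0.772 | 0.77 |
| 0.7 | 0.60 | 0.51 × 1.029 = 0.525 | 0.875 |
| 0.8 | 0.40 | 0.36 × 1.029 = 0.371 | 0.93 |
| 0.9 | 0.20 | 0.19 × 1.029 = 0.196 | 0.98 |

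The ratio reaches 1 at r = 2 × 34/35 − 1 = 0.943. At r = 0.5, 45 × 0.772 = 34.7, so about 35 participants with adjustment would match 45 on change scores.

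**Unequal SDs.** At k = 0.8 the ratios for the same four correlations are 0.59, 0.65, 0.66 and 0.63. At k = 1.25 they are 0.92, 1.01, 1.03 and 0.98. The worst case is b = 1 (for example k = 1.25, r = 0.8): both variances are 0.5625 before the penalty, so the ratio is 35/34 = 1.029. In general, adjustment gains when |1 − b| exceeds s/√34 = 0.17s.

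**Power of the MCP step, by simulation.** Assumed: equal SDs, pooled variance, one-sided 2.5%, and a linear difference of 1.0 baseline SD from 10 to 90 minutes. Change versus adjusted: 55% and 66% at r = 0.5; 76% and 82% at r = 0.7; 90% and 92% at r = 0.8; no difference at r = 0.9. Type I error was 2.2% to 2.6% for both methods.

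**Dose-specific variances, by simulation.** Assumed: residual SD doubling from 10 to 90 minutes, and a generalized least squares linear trend using the full covariance matrix of the dose means.

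| Setting | Slope fitted once by OLS | Slope reweighted iteratively |
|---|---|---|
| k = 1, r = 0.5 | 0.72 | 0.79 |
| k = 1, r = 0.7 | 0.83 | 0.92 |
| k = 1, r = 0.8 | 0.88 | 0.98 |
| k = 1, r = 0.9 | 0.94 | 1.04 |
| k = 1.25, r = 0.8 (b = 1) | 1.00 | 1.11 |

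Each dose-specific variance has only 4 degrees of freedom, so feeding those weights back into the slope adds noise.

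**The case against.** The strongest reply is that nothing in the plan is wrong. Doses are randomized, the change score is unbiased, and its type I error is correct under pooled variance. A reader might infer from the missing covariate that the analysis is biased or invalid; the documents do not support that. This reply stands and limits the point to efficiency.

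Second, the gain cannot be established. Section 10.0 says "The study will take up to two hours and thirty minutes", so both recordings fall in one visit and a slope near 1 is quite possible. In that case there is nothing to gain. This also stands: a reader should not take the 23% reduction at r = 0.5 as a forecast.

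Third, the small worst-case cost holds only with pooled variance or a slope fitted once, whereas the plan's own remark on underweighting points towards dose-specific weights. That is correct, and the fix has to cover it.

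Fourth, it is tempting to justify a common slope from the timing rule in Section 3.0, "This is to ensure that all participants have the same lapse of time between pre- and post-stimulation recording". That does not follow: equal intervals do not show that 10 and 90 minutes of active stimulation leave the same slope, and five per dose cannot check it. The common slope is only a working model; randomization is what protects the dose comparison from bias.

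Finally, critical values need calibration if dose-specific variances are used. That applies equally to change scores and is a separate issue, not part of this point.

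**Conclusion.** The point holds as a recommendation on efficiency, with medium confidence. The plan leaves out a baseline that it collects, and the analysis it describes remains valid without it. With pooled variance and equal SDs, adjustment would cut the variance of a dose contrast by about 23%, 12.5%, 7% and 2% at r = 0.5, 0.7, 0.8 and 0.9; at a slope of exactly 1 it would add about 3%. All these figures rest on assumed correlations and SDs, and the true values will differ by measure. The case for adjusting is the asymmetry between a possibly useful gain and a small, bounded loss. Most of the scatter comes from having five people per dose and remains either way. Measures with no pre-stimulation value are not affected.

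**What to change.** Add to the Analyses paragraph of Section 12.0:
- For every measure with a pre-stimulation value, MCP-Mod will use the dose means and their covariance matrix from a linear model with dose group as factor and that measure's own baseline as covariate, with one common slope as a working model. The response may stay pre- to post-stimulation change, since the dose contrasts are identical to those for the post value.
- State whether residual variance is pooled or dose-specific, so that it agrees with the power paragraph's remark on underweighting. If it is dose-specific, fit the common slope once by ordinary least squares and do not reweight it.

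The cost is a few sentences, one error degree of freedom (36 to 35), and about 3% in variance at worst under pooled variance. With dose-specific variance, the simulated ratio at a slope of 1 was about 1.00 with the slope fitted once and about 1.11 with iterative reweighting. No new data are needed. Fixing this before the data are analysed also removes a later choice between two analyses.
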